6.3. Screen Failure

Subjects will be allowed to repeat any screening procedure once, as long as the results of the repeated procedure will be available within the screening visit window. This will not be considered a screen failure. The period from the start of the screening visit to the baseline visit must not exceed 63 days, inclusive of any repeated procedures.

A subject who is a screen failure at the Screening Visit/Visit 1 or at the Baseline Visit/Visit 2 may be rescreened once. During the rescreening period, subjects will be allowed to repeat any screening procedure once, as long as the results of the repeated procedure will be available within the screening visit window. The period from the start of the rescreening visit to the baseline visit must not exceed 63 days, inclusive of any repeated procedures.

Subjects may only be rescreened once.

7. PRIOR AND CONCOMITANT MEDICATION

The start and stop date, dose, unit, frequency, route of administration, and indication for prior medications and concomitant medications taken within the past 30 days will be recorded.

In addition, all prior treatments for FSGS will be recorded with start and stop date, dose, unit, frequency and route of administration.

7.1. Prohibited Concomitant Medications

The following treatments will not be permitted during the study:

- Any long-acting corticotropin other than IMP.
- Any enteral or parenteral corticosteroid use (topical, inhaled and intra-articular corticosteroids are allowed).
- Administration of live or live-attenuated vaccines.
- Enteral or parenteral immunosuppressive medications including, but not limited to methotrexate, azathioprine, cyclophosphamide, cyclosporine, tacrolimus, MMF, rituximab (or other B-cell inhibitors), and tumor necrosis factor inhibitors (eg, Enbrel[®], Humira[®], Remicade[®]); intraocular immunosuppressive medications are allowed.
- Any investigational drug, device, or procedure administered as part of a research study.

If any prohibited medication is taken during the study, all pertinent information will be recorded in source documents and the electronic case report form (eCRF). The designated study MM must be informed immediately so the sponsor may determine whether to continue the subject in the study.

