	
• [REDACTED]■ [REDACTED]■ [REDACTED]■ [REDACTED]■ [REDACTED]■ [REDACTED]■ [REDACTED]■ [REDACTED]■ [REDACTED]■ [REDACTED]■ [REDACTED]■ [REDACTED]
Entry Criteria: Male or nonpregnant, nonlactating female subjects 18 years of age or older with primary FSGS (confirmed by renal biopsy) who are nephrotic (uPCR > 3.0 mg/mg and estimated glomerular filtration rate [eGFR] at least 30 mL/min/1.73 m ²) and who have failed to achieve sustained CR or PR of proteinuria with at least 1 prior immunosuppressive therapy OR intolerance at least 1 prior immunosuppressive therapy will be enrolled in the study. Subjects must be treated with an angiotensin converting enzyme inhibitor or angiotensin receptor blocker (or have documentation of intolerance), for at least 4 weeks prior to Screening Visit/Visit 1 with blood pressure no more than 150/90. Subjects also must be negative for hepatitis B, hepatitis C, have no history of tuberculosis (TB) or other contraindication as per the United States (US) Prescribing Information for Acthar, have no history of Type 1 or Type 2 diabetes mellitus, or have any clinically significant infection. Subjects cannot have taken Rituximab or cyclophosphamide 24 weeks prior to Screening Visit/Visit 1, any investigational treatments for FSGS or oral corticosteroids (unless used to treat FSGS) for 12 weeks prior to Screening Visit/Visit 1, any intravenous/intramuscular corticosteroids (unless used to treat FSGS) for 8 weeks prior to Screening Visit/Visit 1, or have been involved in a therapeutic drug/device trial (other than for FSGS) 4 weeks prior to Screening Visit/Visit 1.	
Concomitant Medications and Treatments: A stable dose of angiotensin-converting enzyme inhibitor/ angiotensin receptor blocker is required throughout study participation. Subjects requiring other antihypertensive medications must be on a stable dose at least 4 weeks prior to the first dose of Acthar. Subjects are not permitted to take any enteral or parenteral corticosteroid, live or live-attenuated vaccine or systemic immunosuppressive medication during the study. All medications and nondrug therapies (eg, blood transfusions, oxygen supplementation) at Screening Visit/Visit 1 and throughout the study will be recorded.	

Study Title: Treatment of Proteinuria Due to Treatment Resistant or Treatment Intolerant Idiopathic Focal Segmental Glomerulosclerosis: A Prospective Study of Acthar (PODOCYTE)	

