13. Has a clinically significant infection requiring intravenous administration of antibiotics and hospitalization in the 4 weeks prior to Screening Visit/Visit 1.
14. Has known immune compromised status, including but not limited to, individuals who have undergone organ transplantation or who are known to be positive HIV.

15. Has Type 1 or Type 2 diabetes mellitus (prior diagnosis of gestational diabetes mellitus is not exclusionary).
16. Has had any of the following in the 12 weeks prior to Screening Visit 1/Visit 1: unstable angina confirmed by a cardiologist, myocardial infarction, coronary artery bypass graft, percutaneous trans-luminal coronary angioplasty, transient ischemic attack or cerebrovascular disease, unstable cardiac arrhythmia, or resuscitated sudden cardiac death.
17. Has any solid tumor malignancy currently diagnosed or undergoing therapy, or has received therapy for any solid tumor malignancy in the 5 years prior to Screening Visit/Visit 1, with the exception of treated and cured basal cell carcinoma, treated and cured squamous cell carcinoma of the skin, and treated and cured carcinoma in situ of the cervix.
18. Has a diagnosis of, is undergoing therapy for, or has received therapy for a hematologic malignancy in the 5 years prior to Screening Visit/Visit 1.
19. Has been treated with any of the medications outlined in [Table 2](#) within the specified timeframe prior to the Screening Visit/Visit 1.

Table 2: Prohibited Medications Relative to Screening Visit/Visit 1

24 weeks before Screening Visit/Visit 1	12 weeks before Screening Visit/Visit 1	8 weeks before Screening Visit/Visit 1	4 weeks before Screening Visit/Visit 1
Rituximab	Investigational treatment for FSGS	Intravenous/intramuscular corticosteroids ^{a, c}	Therapeutic drug/device trial (except FSGS)
Cyclophosphamide	Chronic oral corticosteroids ^{a,b}		
^a Does NOT include corticosteroids (enteral or parenteral) used for the treatment of FSGS. ^b Chronic use is defined as any dose of corticosteroid taken > 4 consecutive weeks. ^c Any dose of parenteral corticosteroids 8 weeks prior to Screening Visit/Visit 1.			

20. Has been treated with any of the medications outlined in [Table 3](#) within the specified timeframe prior to Baseline Visit/Visit 2.

Table 3: Prohibited Medications Relative to Baseline Visit/Visit 2

FSGS Treatment at Screening Visit/Visit 1 ^a	Days Prior to Baseline/Visit 2
CNI	> 49 days
Corticosteroids ^b , Mycophenolate, Mofetil	> 30 days

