^a If subject is not currently receiving immunosuppressant treatment for FSGS at the Screening Visit/Visit 1, the Baseline Visit/Visit 2 will occur >2 days and < 63 days after the Screening Visit/Visit 1. ^b Corticosteroids used for the treatment of FSGS (see exclusion Criterion 14 for corticosteroid use to treat other conditions).	

21. Has current or recent (within 6 months of the Screening Visit/Visit 1) drug or alcohol abuse as defined in Diagnostic and Statistical Manual of Mental Disorders, Fifth Edition, Diagnostic Criteria for Drug and Alcohol Abuse ([American Psychiatric Association, 2013](#)).
22. Has any of the following laboratory abnormalities at the Screening Visit/Visit 1:
- Hemoglobin \leq 8.0 g/dL.
 - Platelets \leq 50,000 cells/ μ L.
 - Absolute neutrophil count (ANC) \leq 1,000 cells/ μ L.
 - Aspartate aminotransferase (AST), alanine aminotransferase (ALT), or total bilirubin $>$ 2 times the upper limit of normal (ULN).
 - Glycosylated hemoglobin (HbA1c) $>$ 6.5%.
 - Positive Hepatitis B surface antigen (HBsAg) or Hepatitis B core antibody (HBcAb).
 - Positive Hepatitis C virus antibody (HCV) and HCV polymerase chain reaction (PCR) \geq 25 IU/mL (HCV PCR will be automatically analyzed if HCV is positive).
 - Positive or indeterminate interferon gamma release assay (IGRA).
23. Has any other clinically significant disease, disorder or laboratory abnormality (including those listed on the Prescribing Information Section 5: Warnings and Precautions [[Mallinckrodt ARD LLC, 2015](#)]) which, in the opinion of the investigator (by its nature or by being inadequately controlled), might put the patient at risk due to participation in the study, or may influence the results of the study or the subject's ability to complete the study.

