8.1. Screening Visit/Visit 1 (Study Days -63 to -3) Procedures

Screening assessments must be performed within 3 to 63 days prior to the Baseline Visit/Visit 2.

The following procedures will be performed at the Screening Visit/Visit 1:

- Informed consent.
 - Note: Subjects (US only) with stored renal biopsy samples will be re-consented after implementation of Amendment 3 to allow for sponsor contact and permission for additional sample examination.
 - Inclusion/exclusion criteria.
 - Contact the Interactive Phone/Web Response System (IXRS).
 - Medical and surgical history.
 - Current medical condition review.
 - Demographics.
 - Vital signs.
 - Height and Weight.
 - Complete physical examination.
 - Clinical laboratory tests.
 - [REDACTED]
 - HbA1c.
 - Serum pregnancy test.
 - Hepatitis serology.
 - IGRA test for TB (to be performed locally).
 - Urinalysis.
 - [REDACTED]
 - [REDACTED]
- NOTE: A separate consent is required for this procedure.
- Dispense 24-hour urine collection materials.
 - Adverse events (AEs) and concomitant medications.

Subjects who are taking immunosuppressant medication for FSGS at the time of the Screening Visit/Visit 1 must discontinue their use and complete a washout period of appropriate length before the Baseline Visit/Visit 2 ([Table 4](#)).

Table 4: Timing of Baseline Visit/Visit 2 Relative to FSGS Treatment at Screening

FSGS Treatment at Screening Visit/Visit 1	Timing of Baseline Visit/Visit 2
CNI	> 49 days and < 63 days after drug discontinuation
Corticosteroids, MMF	> 30 days and < 63 days after drug discontinuation
No treatment	Eligibility is confirmed and IMP is on-site.

Subjects will be allowed to repeat any screening procedure, if necessary, if it is within the screening time window. A screening procedure can be repeated only once; if the repeat procedure continues to be exclusionary, the subject will be a screen failure.

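### The 24-week pre-Screening exclusion names rituximab but not the other B-cell inhibitors that Section 7.1 groups with it, and several other banned immunosuppressants have no stated interval

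*Combined protocol and SAP*

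**What the plan says.** The on-study ban in Section 7.1 is an open list of enteral and parenteral immunosuppressants. It names "methotrexate, azathioprine, cyclophosphamide, cyclosporine, tacrolimus, MMF, rituximab (or other B-cell inhibitors), and tumor necrosis factor inhibitors".

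The pre-study rules are narrower:

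- **Synopsis and Table 2 (Section 6.2).** The synopsis states: "Subjects cannot have taken Rituximab or cyclophosphamide 24 weeks prior to Screening Visit/Visit 1". The 24-week column of Table 2 holds the same two drugs. Its 12-week column includes "Investigational treatment for FSGS", and its 4-week column covers participation in a non-FSGS trial.
- **Table 3 (Section 6.2) and Table 4 (Section 8.1).** Both are headed by FSGS treatment at Screening. Both give more than 49 days for CNI and more than 30 days for corticosteroids and MMF.
- **Section 8.1, text.** Subjects taking an immunosuppressant for FSGS at Screening "must discontinue their use and complete a washout period of appropriate length before the Baseline Visit/Visit 2". Table 4 is given as the source of the length.
- **Table 3, footnote a.** "If subject is not currently receiving immunosuppressant treatment for FSGS at the Screening Visit/Visit 1, the Baseline Visit/Visit 2 will occur >2 days", and within 63 days. In Table 4 the same subjects fall under no treatment: Baseline follows once eligibility is confirmed and drug is on site.
- **Section 7.** All prior FSGS treatments are recorded. Other medications are recorded for the past 30 days.

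**The concern.** The protocol itself puts rituximab and other B-cell inhibitors together when it bans them on study, then separates them at entry without giving a reason. Followed as written, the entry rules admit a subject recently treated with a non-rituximab B-cell inhibitor.

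This matters because the study has one arm and its primary endpoints are safety endpoints (Section 4.1). Section 3.5 lists increased infection risk among the known risks of Acthar. An infection after the first dose that owed something to earlier immunosuppression would count as treatment-emergent and enter the summaries of Section 12.7.1, with no control arm to set it against. Under Section 12.6.3 concomitant medications are listed but not summarised, so the summary tables would not show the earlier exposure. There is also a direct safety question: the subject could carry the overlapping immunosuppression that Section 7.1 is meant to prevent.

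**Working it through.** The plan gives no figure of its own on this point. The check sets each entry of Section 7.1 against the pre-study rules, for use outside a trial.

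| Entry in Section 7.1 | FSGS treatment at Screening | Use for another disease |
|---|---|---|
| Rituximab | 24 weeks before Screening | 24 weeks before Screening |
| Cyclophosphamide | 24 weeks before Screening | 24 weeks before Screening |
| Cyclosporine, tacrolimus (CNI) | more than 49 days before Baseline | none stated |
| MMF | more than 30 days before Baseline | none stated |
| Other B-cell inhibitors | washout required, no length given | none stated |
| Methotrexate, azathioprine | washout required, no length given | none stated |
| TNF inhibitors | washout required, no length given | none stated |

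That is nine entries. Two have an interval whatever the indication. Three (cyclosporine, tacrolimus, MMF) have one only as FSGS treatment at Screening. Four have none.

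**Rituximab or cyclophosphamide, minimum time from last dose to first Acthar dose**
- 24 weeks × 7 = 168 days before Screening.
- Shortest Screening-to-Baseline gap: more than 2 days, so 3 days (Table 3 footnote a; Section 8.1).
- 168 + 3 = 171 days.

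**Another B-cell inhibitor, outside a trial, stopped at or just before Screening**
- If it is not ongoing FSGS treatment at Screening, the Section 8.1 washout does not apply and the subject counts as untreated.
- The only stated minimum is the 3-day gap. It is a theoretical floor, because screening results and drug supply must be in hand first.
- The Screening-to-Baseline limit of 63 days (Section 6.3) caps the wait.
- The interval is therefore about 3 to 63 days, decided by logistics and not by the drug.

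**The same agent inside a trial**
- Investigational FSGS treatment: 12 × 7 + 3 = 87 days.
- Non-FSGS trial: 4 × 7 + 3 = 31 days.
- Trial use therefore has a floor where ordinary prescribed use has none.

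**Weight of one subject.** With about 60 subjects, one affected subject with an infection moves a crude event percentage by 1/60 = 1.7 points. How many subjects would be affected, and how much of any infection would be carry-over, cannot be derived from the documents.

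**The case against.** The strongest reply is that a washout table need not mirror an on-study ban. Tables 3 and 4 cover the drugs that Section 3.1 describes as recommended FSGS therapy: corticosteroids, CNI and MMF. Section 3.1 does not present methotrexate, azathioprine or TNF inhibitors as FSGS treatment. Other rules also help. Exclusion 13 removes recent serious infection, and exclusion 22 screens neutrophils, hepatitis and TB. Exclusion 14 covers a subject who "Has known immune compromised status, including but not limited to, individuals who have undergone organ transplantation". Exclusion 23 lets the investigator exclude for a condition that "might put the patient at risk due to participation in the study, or may influence the results of the study". All of this stands as mitigation, but none of it sets an interval, and the sponsor did not rely on it alone for rituximab or cyclophosphamide.

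Four stronger readings are tempting, and the documents do not support them:

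- **A measured shortfall.** Setting 63 days against 171, a reader might infer that the plan is 108 days, or 63%, short. No documented requirement is missed: the plan nowhere says that every B-cell inhibitor needs 24 weeks, and the only pharmacological reason given for a 24-week entry (summary of changes) concerns cyclophosphamide. The comparison also assumes a last dose at Screening.
- **A rule that cannot be checked.** The 30-day look-back might suggest this. But eligibility is reviewed at both visits, subject information goes into source documents (Section 18.1), and FSGS treatments are recorded without a time limit. What remains is that, for non-FSGS use, the protocol's medication record does not reach back 24 weeks.
- **A ready-made default.** The 49 days for CNI might seem a natural interval for the other agents. The documents give no clinical basis for it, and it would ask more of azathioprine than the 30 days asked of MMF.
- **A distorted result.** Causality grading (Table 7) allows for concomitant medication and clinical state, related events are summarised separately, and about 60 subjects can be reviewed case by case. The safety analysis is descriptive, so no decision rule is at risk.

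**Conclusion.** The gap is real and can be read directly from the text. The 24-week exclusion omits the class that Section 7.1 joins to rituximab, and a subject recently given another B-cell inhibitor outside a trial can be enrolled with no stated minimum beyond more than 2 days from Screening to Baseline. Methotrexate, azathioprine and TNF inhibitors have no interval either, nor do CNI and MMF taken for another disease.

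Severity is minor to moderate. Few subjects are likely to be affected, and the effect on the safety results cannot be sized from the documents. Confidence is high for the textual gap and low for its consequence.

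The conclusion rests on two readings: that the headings of Tables 3 and 4 limit them to FSGS treatment at Screening, and that the on-study ban does not reach a drug stopped before consent. The case for 24 weeks for the whole class rests on the sponsor's own grouping in Section 7.1, not on pharmacological data in the documents.

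**What to change.** 1. In Table 2 and the matching synopsis sentence, change *Rituximab* to *Rituximab or other B-cell inhibitors*, at 24 weeks before Screening.
2. In Section 7, record systemic immunosuppressants for any indication back to 24 weeks before Screening, so that the rule can be verified in the eCRF and earlier exposure is visible when infections are reviewed.
3. Secondary: add to Table 3 a row for any systemic immunosuppressant prohibited by Section 7.1, for any indication, including CNI and MMF for non-FSGS use. The sponsor's clinical team should set agent-specific lengths. An agent that needs more than the 63 days available between Screening and Baseline belongs in Table 2.

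The stop-and-wash-out instruction in Section 8.1 should stay limited to FSGS treatment, so that a patient who needs one of these drugs for another disease is excluded and not told to stop it. Intraocular agents stay allowed.

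The cost is a few words in Table 2 and the synopsis, one line in Section 7 and one row in Table 3. A few subjects would wait longer or be excluded.

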7.2. Permitted During Study

If any medication is taken during the study, all pertinent information will be recorded in source documents and the eCRF.

Subjects should remain on stable doses of ACEi and/or ARB during the study. An adjustment in the dose of these medications would represent a protocol deviation, but would not necessarily mandate study termination. Adjustments in dose of a concomitant medication should be documented in the subject's source documents and eCRF.

8. PROCEDURES

The schedule of study procedures is summarized in the Schedule of Study Events ([Table 1](#)).

8.1. Screening Visit/Visit 1 (Study Days -63 to -3) Procedures

Screening assessments must be performed within 3 to 63 days prior to the Baseline Visit/Visit 2.

The following procedures will be performed at the Screening Visit/Visit 1:

- Informed consent.
 - Note: Subjects (US only) with stored renal biopsy samples will be re-consented after implementation of Amendment 3 to allow for sponsor contact and permission for additional sample examination.
 - Inclusion/exclusion criteria.
 - Contact the Interactive Phone/Web Response System (IXRS).
 - Medical and surgical history.
 - Current medical condition review.
 - Demographics.
 - Vital signs.
 - Height and Weight.
 - Complete physical examination.
 - Clinical laboratory tests.
 - [REDACTED]
 - HbA1c.
 - Serum pregnancy test.
 - Hepatitis serology.
 - IGRA test for TB (to be performed locally).
 - Urinalysis.
 - [REDACTED]
 - [REDACTED]
- NOTE: A separate consent is required for this procedure.
- Dispense 24-hour urine collection materials.
 - Adverse events (AEs) and concomitant medications.

Subjects who are taking immunosuppressant medication for FSGS at the time of the Screening Visit/Visit 1 must discontinue their use and complete a washout period of appropriate length before the Baseline Visit/Visit 2 ([Table 4](#)).

Table 4: Timing of Baseline Visit/Visit 2 Relative to FSGS Treatment at Screening

FSGS Treatment at Screening Visit/Visit 1	Timing of Baseline Visit/Visit 2
CNI	> 49 days and < 63 days after drug discontinuation
Corticosteroids, MMF	> 30 days and < 63 days after drug discontinuation
No treatment	Eligibility is confirmed and IMP is on-site.

Subjects will be allowed to repeat any screening procedure, if necessary, if it is within the screening time window. A screening procedure can be repeated only once; if the repeat procedure continues to be exclusionary, the subject will be a screen failure.

8.2. Baseline Visit/Visit 2 Procedures

The timing of the Baseline Visit/Visit 2 will depend on the washout period for the immunosuppressives the subject is taking at screening. The subject will collect a 24-hour urine 3 days prior (± 2 days) to Baseline Visit/Visit 2.

The investigator or designee will complete the following procedures at the Baseline Visit/Visit 2:

- Inclusion/exclusion criteria review; subject must meet all eligibility criteria at Screening Visit/Visit 1 *and* Baseline Visit/Visit 2.
- Current medical condition review.
- Limited physical examination.
- Vital signs.
- Weight (height from Visit 1 will be used to calculate BMI at Visit 2).
- Clinical laboratory tests.
- Nonfasting lipid panel.
- [REDACTED]
- Urine pregnancy test.
- Urinalysis.
- [REDACTED]
- [REDACTED]
- [REDACTED]
- [REDACTED]
- [REDACTED]
- Subject diary training.
- Contact IXRS and dispense IMP kits.
- IMP administration under supervision of study staff and observation for at least 1 hour thereafter.
- AEs and concomitant medications.

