1.4. Schedule of Study Events

Table 1: Schedule of Study Events

Period	Screening (Day -63 to -3)	Baseline	Open Label/Open-label Extension													Taper Safety Visit ^a	End of Study/Early Termination ^b
			3	4	5	6	7	8	9	10	11	12	13	14	15		
VISIT #: Visit window is ± 5 days starting with Visit 2 (except at V9 where window is + 5 days only)	1	2															
Week		0	4	8	12	16	20	24	26	30	34	38	42	46	50		54 or 56
Informed consent ^c	X																
Inclusion/exclusion criteria review	X	X															
Demographics	X																
Medical/surgical history	X																
Current medical condition review	X	X	X	X	X	X	X	X	X	X	X	X	X	X	X	X	X
Complete physical examination	X																
Limited physical examination		X	X	X	X	X	X	X	X	X	X	X	X	X	X	X	
Vital signs	X	X	X	X	X	X	X	X	X	X	X	X	X	X	X	X	X
Height (screening only) and weight	X	X	X	X	X	X	X	X	X	X	X	X	X	X	X	X	X
Clinical laboratory tests (serum chemistry and CBC w/diff)	X	X	X	X	X	X	X	X		X	X	X	X	X	X	X ^d	X
HbA1c	X				X			X				X			X		
Nonfasting lipid panel		X			X			X				X			X		
██████████		X		X		X		X			X		X		X		
██████	X	X		X		X		X			X		X		X		

Period	Screening (Day -63 to -3)	Baseline	Open Label/Open-label Extension													Taper Safety Visit ^a	End of Study/Early Termination ^b
			3	4	5	6	7	8	9	10	11	12	13	14	15		
VISIT #: Visit window is ± 5 days starting with Visit 2 (except at V9 where window is + 5 days only)	1	2	3	4	5	6	7	8	9	10	11	12	13	14	15		
Week		0	4	8	12	16	20	24	26	30	34	38	42	46	50		54 or 56
██████████	X																
████████████████████		X		X		X		X			X		X		X		
Serum pregnancy test	X																
IGRA for TB	X																
██████████	X	X		X		X		X			X		X		X		X
Urine pregnancy test		X	X	X	X	X	X	X	X	X	X	X	X	X	X	X	X
██████████	X	X	X	X	X	X	X	X	X	X	X	X	X	X	X		
████████████████████ ^s	X						X							X			
██████████		X						X							X		
██████████	X																
IXRS contact	X	X	X	X	X	X	X	X	X	X	X	X	X	X	X	X	X
IMP and diary training		X						X							X ^f		
IMP accountability			X	X	X	X	X	X	X	X	X	X	X	X	X	X	X ^f
Dispense IMP kits		X	X	X	X	X	X	X	X	X	X	X	X	X	X ^f		
Administer first dose ^g		X															
Diary review			X	X	X	X	X	X	X	X	X	X	X	X	X	X	X
██████████		X						X							X		

Period	Screening (Day -63 to -3)	Baseline	Open Label/Open-label Extension													Taper Safety Visit ^a	End of Study/Early Termination ^b	
			3	4	5	6	7	8	9	10	11	12	13	14	15			
VISIT #: Visit window is ± 5 days starting with Visit 2 (except at V9 where window is + 5 days only)	1	2																

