therapy. Seventy percent of adults with primary FSGS will have nephrotic range proteinuria ([Kitiyakara et al, 2003](#)). The initial Kidney Disease Improving Global Outcomes (KDIGO) recommended immunosuppressive therapy for most adults with primary FSGS is oral prednisone, with calcineurin inhibitors (CNI) reserved for those at high risk for glucocorticoid-induced toxicity. There is no universal agreement on the dose and duration of prednisone therapy, though the current KDIGO Clinical Practice Guidelines for glomerulonephritis recommends treatment with high doses of prednisone, 1 mg/kg/day or 2 mg/kg every other day, for between 4 and 16 weeks or until CR. If CR occurs, prednisone is then tapered slowly over a 6-month period. If the FSGS is steroid resistant, the KDIGO recommended second-line treatment is a CNI for 4 to 6 months, although CNI are not FDA-approved for this indication. If PR or CR occurs, it is recommended that the CNI be slowly tapered over at least 12 months. A combination of mycophenolate mofetil (MMF) and high dose dexamethasone is the KDIGO recommended alternative for patients who do not tolerate or respond to the CNI, although MMF is also not FDA-approved for this indication ([KDIGO Work Group, 2012](#)).

About 50% of patients with primary FSGS will be resistant to therapy with corticosteroids ([Bose and Cattran, 2014](#)). The prolonged duration of high doses of prednisone is frequently associated with significant side effects including the development or worsening of diabetes, weight gain, fluid retention, osteoporosis, behavioral changes, and infection. Between 30% and 40% of patients resistant to steroids will also be resistant to CNIs, and in those who respond, relapse is common ([Cattran et al, 2007](#)). CNIs are also associated with significant side effects, such as hypertension and glucose intolerance, and the long-term nephrotoxicity associated with their use may potentially abrogate the benefit from the reduction in proteinuria. These side effects make a number of patients with FSGS intolerant to the therapies. Thus a significant unmet need for efficacious therapies exists for both children and adults diagnosed with primary FSGS.

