4. OBJECTIVES

4.1. Primary Objective

Primary Objective	Primary Endpoints
To confirm the safety and tolerability of Acthar in the induction of remission of proteinuria in subjects with primary FSGS who are resistant to, or intolerant of, at least 1 prior immunosuppressive therapy	
 ● Severity and frequency of adverse events (AEs) ● Changes in physical findings ● Changes in clinical laboratory findings ● Changes in vital signs

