24. ATTACHMENTS

24.1. Attachment 1: Clinical Laboratory Tests

Serum Chemistry	
Alanine aminotransferase (ALT)	Creatinine
Albumin (total)	Cystatin C
Alkaline phosphatase	Glucose
Aspartate aminotransferase (AST)	Hemoglobin A1c
Bilirubin (total)	Phosphorus
Blood urea nitrogen	Potassium
Calcium	Protein, total
CO ₂	Sodium
Chloride	Uric acid
Lipid Panel	
Total cholesterol	LDL
HDL	Triglycerides
Hormones	
Serum and urine beta-human chorionic gonadotropin (pregnancy test)	
Hematology Assays	
Hematocrit	Platelet count
Hemoglobin	Red blood cell count
White blood cell count, including differential	Absolute neutrophil count
Urinalysis	
Blood	Nitrite
Clarity	Nitrite
Color	Protein
Glucose	pH
Leukocyte esterase	Specific gravity
Ketones	

Serum Chemistry	
Hepatitis Serology	
Hepatitis B core antibody	Hepatitis C virus antibody (HCV)
Hepatitis B surface antigen	Hepatitis C virus PCR (only if HCV +)
TB Assay	
Interferon gamma release assay (IGRA) (obtained at local lab)	

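### HbA1c has no scheduled Baseline sample, and Attachment 1 conflicts with that; if Screening is the reference, a rise on Acthar can be understated in subjects who wash out a CNI or corticosteroid

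*Combined protocol and SAP*

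**What the plan says.** **Schedule.** Table 1 gives HbA1c its own row, marked at Screening and at Visits 5, 8, 12 and 15 (Weeks 12, 24, 38 and 50). The Baseline cell is empty. The visit lists agree: Sections 8.1, 8.5, 8.8, 8.12 and 8.15 name HbA1c as a line separate from the clinical laboratory tests, and the readable items of Section 8.2 do not include it. Section 10 also names HbA1c separately from chemistry.

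**Attachment 1.** Section 24.1 lists "Hemoglobin A1c" in the serum chemistry block. Section 10.7 says that the clinical laboratory tests are those in Section 24.1, and the Table 1 row that begins "Clinical laboratory tests (serum chemistry and CBC w/diff" is marked at Baseline. Read literally, that would put HbA1c in the Baseline draw.

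**Washout.** Under Section 8.1, subjects taking immunosuppressants for FSGS at Screening "must discontinue their use and complete a washout period of appropriate length" before Baseline. Section 8.2 adds: "The timing of the Baseline Visit/Visit 2 will depend on the washout period for the immunosuppressives the subject is taking at screening". Table 4 sets the wait at more than 49 and less than 63 days for a CNI, and more than 30 and less than 63 days for corticosteroids or MMF.

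**Glycaemic effect of the earlier drugs.** Section 3.1 says that "CNIs are also associated with significant side effects, such as hypertension and glucose intolerance", and that prolonged high-dose prednisone is "frequently associated with significant side effects including the development or worsening of diabetes". It gives no sizes.

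**Use of the data.** One of the four primary endpoints in Section 4.1 is "Changes in clinical laboratory findings". Section 12.7.2 plans data listings only for laboratory tests. Section 12 defines no laboratory baseline.

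**The concern.** Hyperglycaemia is among the known risks of Acthar in Section 3.5, and HbA1c is the scheduled measure of sustained glycaemia. A change needs a reference. If Table 1 is followed, the Screening value is the only HbA1c before dosing.

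For a subject on a CNI or corticosteroid at Screening, that value was taken on a drug that the protocol itself links to worse glycaemia. The drug is then stopped. The whole washout falls between the reference and the first on-treatment HbA1c, so any fall after stopping is subtracted from any rise on Acthar. The study has a single arm, so no control group shows the drift. Section 10.7 also asks investigators to report clinically significant changes in laboratory values as AEs, so the choice of reference could reach the AE counts too.

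**Working it through.** The plan states no HbA1c effect, SD or sample-size calculation, so there is no figure of its own to reproduce.

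**1. Which reading of the schedule is better supported?** Table 1, five visit lists and Section 10 treat HbA1c as separate from chemistry. If it belonged to the chemistry panel, its own row would be redundant and it would be drawn at nearly every visit. Redaction is an unlikely explanation for the gap in Section 8.2, because the Table 1 row is legible and HbA1c is printed openly at the other visits. The schedule is therefore the likelier instruction, but Attachment 1 contradicts it.

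**2. Intervals (Tables 1 and 4, Section 6.3).** Screening to Baseline is at most 63 days. Week 12 is day 84 ± 5, that is, day 79 to 89.

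| At Screening | Days off drug at Baseline | Screening HbA1c to Week 12 HbA1c, days |
|---|---|---|
| CNI | 50 to 62 | 50 + 79 = 129 to 63 + 89 = 152 |
| Corticosteroid | 31 to 62 | 31 + 79 = 110 to 152 |
| No treatment | not applicable | 3 + 79 = 82 to 152 |

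**3. Model (assumed, not in the documents).** HbA1c weights past glucose linearly over a red-cell life of L = 120 days, and the earlier drug's effect on glucose ends when it is stopped. The share of the excess d still present t days after stopping is (1 - t/120)².

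- 31 days: (89/120)² = 0.55
- 50 days: (70/120)² = 0.34
- 62 days: (58/120)² = 0.23
- 110 days, the earliest Week 12 sample: (10/120)² = 0.007
- 115 days (31 + 84, nominal Week 12): (5/120)² = 0.002

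With L = 90 days, 43% of d remains at 31 days, 10% at 62 days, and none by Week 12.

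**4. Change at nominal Week 12 for a true rise of 0.3 points.** The assumed d is 0.3 to 0.8 points.

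- From Screening: 0.3 - d × (1 - 0.002). For d = 0.3 this is about 0.0; for d = 0.8 it is about -0.5.
- From a Baseline value after 31 days: 0.3 - d × (0.550 - 0.002) = +0.14 for d = 0.3 and -0.14 for d = 0.8.
- From a Baseline value after 50 days: 0.3 - 0.34d = +0.20 and +0.03.
- From a Baseline value after 62 days: 0.3 - 0.234d = +0.23 and +0.11.

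A Baseline sample therefore removes 45% to 77% of the carry-over (1 - 0.55 to 1 - 0.23), not all of it.

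**5. Cohort mean.** If a share s of subjects is affected, the mean change from Screening is too low by about s × d. For d of 0.3 to 0.8 this is 0.03 to 0.08 points at s = 10%, 0.075 to 0.20 at 25%, and 0.15 to 0.40 at 50%. These values of s are assumptions.

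**The case against.** The strongest reply is that the plan contains no analysis that could be biased. Laboratory data are only listed, and no text makes Screening the HbA1c reference. That stands as far as it goes: the understatement arises only if someone reads change from Screening. But the primary endpoint is a change, and under the schedule a listing would hold no other pre-dose HbA1c to read it from.

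Second, Attachment 1 may mean that HbA1c is drawn at Baseline after all. This also stands in part, so the absence of a sample cannot be stated as certain. If that was the intention, Table 1 and Section 8.2 need correcting instead.

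Third, a reader might infer that the schedule hides glycaemic harm from Acthar. The documents do not support that:

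- Serum glucose is in the chemistry panel and is measured at Baseline after the washout. It is an imperfect substitute, because Section 10.7 allows fasted or nonfasted samples.
- The dose-reduction and discontinuation criteria in Sections 9.3.1 and 9.3.2 use absolute HbA1c and glucose values, so they need no reference.
- Diabetes and a Screening HbA1c above 6.5% are exclusions (Section 6.2), which limits how large d can be.
- All values are listed, so subjects with a washout can be identified.

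Fourth, size and reach are unknown. That is correct, and the figures here are illustrations. The carry-over argument does not apply to subjects with no treatment at Screening. Nor does Section 3.1 attribute a glycaemic effect to MMF.

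**Conclusion.** The point holds in limited form. Table 1 and Section 8.2 schedule no Baseline HbA1c, Attachment 1 conflicts with them, and the passages must be reconciled. If the schedule is followed, change from Screening can understate an Acthar-related rise by about d in subjects who wash out a CNI or corticosteroid. For an assumed d of 0.3 to 0.8 points, a true +0.3 would read about 0.0 to -0.5.

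The direction rests on the protocol's own account of the earlier drugs. The size rests on the assumed d, the red-cell model, and the assumption that the earlier drug's effect ends when it is stopped. The share of subjects affected is not given. It does not follow that the harm would go unseen or that the safety triggers are compromised. This is a cheap improvement to the reference value.

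**What to change.** 1. Add HbA1c to Baseline/Visit 2, before the first dose, in Table 1 and Section 8.2, and bring Attachment 1 into line with the schedule.
2. State that this value is the reference for HbA1c change, and keep the Screening value for eligibility.
3. Present HbA1c change separately for subjects with and without a CNI or corticosteroid washout. Do this for all subjects, including those with the new sample, because a Baseline value still carries 23% to 55% of d under the 120-day model. For subjects already dosed without a Baseline HbA1c, the Screening value remains the reference and should be marked as such.

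The cost is one extra central-laboratory assay per subject not yet dosed (at most about 60), from blood already drawn at that visit, plus one more split in the presentation of HbA1c.
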